5.3.4 Assessment of Causality of Adverse Events

Investigators should use their knowledge of the patient, the circumstances surrounding the event, and an evaluation of any potential alternative causes to determine whether an adverse event is considered to be related to the study drug, indicating "yes" or "no" accordingly. The following guidance should be taken into consideration (see also [Table 5](#)):

- Temporal relationship of event onset to the initiation of study drug
- Course of the event, with special consideration of the effects of dose reduction, discontinuation of study drug, or reintroduction of study drug (as applicable)
- Known association of the event with the study drug or with similar treatments
- Known association of the event with the disease under study

- Presence of risk factors in the patient or use of concomitant medications known to increase the occurrence of the event
- Presence of non-treatment-related factors that are known to be associated with the occurrence of the event

Table 5 Causal Attribution Guidance

Is the adverse event suspected to be caused by the study drug on the basis of facts, evidence, science-based rationales, and clinical judgment?	
YES	There is a plausible temporal relationship between the onset of the adverse event and administration of the study drug, and the adverse event cannot be readily explained by the patient's clinical state, intercurrent illness, or concomitant therapies; and/or the adverse event follows a known pattern of response to the study drug; and/or the adverse event abates or resolves upon discontinuation of the study drug or dose reduction and, if applicable, reappears upon re-challenge.
NO	An adverse event will be considered related, unless it fulfills the criteria specified below. Evidence exists that the adverse event has an etiology other than the study drug (e.g., preexisting medical condition, underlying disease, intercurrent illness, or concomitant medication); and/or the adverse event has no plausible temporal relationship to administration of the study drug (e.g., cancer diagnosed 2 days after first dose of study drug).

5.3.5 Procedures for Recording Adverse Events

Investigators should use correct medical terminology/concepts when recording adverse events on the Adverse Event eCRF. Avoid colloquialisms and abbreviations.

Only one adverse event term should be recorded in the event field on the Adverse Event eCRF.

5.3.5.1 Injection Reactions

Adverse events that occur during or within 24 hours after study drug administration should be captured as individual signs and symptoms on the Adverse Event eCRF rather than an overall diagnosis (e.g., record dyspnea and hypotension as separate events rather than a diagnosis of injection reaction).

5.3.5.2 Diagnosis versus Signs and Symptoms

For adverse events other than injection reactions (see Section 5.3.5.1), a diagnosis (if known) should be recorded on the Adverse Event eCRF rather than individual signs and symptoms (e.g., record only liver failure or hepatitis rather than jaundice, asterixis, and elevated transaminases). However, if a constellation of signs and/or symptoms cannot be medically characterized as a single diagnosis or syndrome at the time of reporting, each individual event should be recorded on the Adverse Event eCRF. If a diagnosis is subsequently established, all previously reported adverse events based on signs and symptoms should be nullified and replaced by one adverse event report based on the

single diagnosis, with a starting date that corresponds to the starting date of the first symptom of the eventual diagnosis.

5.3.5.3 Adverse Events That Are Secondary to Other Events

In general, adverse events that are secondary to other events (e.g., cascade events or clinical sequelae) should be identified by their primary cause, with the exception of severe or serious secondary events. A medically significant secondary adverse event that is separated in time from the initiating event should be recorded as an independent event on the Adverse Event eCRF. For example:

- If vomiting results in mild dehydration with no additional treatment in a healthy adult, only vomiting should be reported on the eCRF.
- If vomiting results in severe dehydration, both events should be reported separately on the eCRF.
- If a severe gastrointestinal hemorrhage leads to renal failure, both events should be reported separately on the eCRF.
- If dizziness leads to a fall and consequent fracture, all three events should be reported separately on the eCRF.
- If neutropenia is accompanied by an infection, both events should be reported separately on the eCRF.

All adverse events should be recorded separately on the Adverse Event eCRF if it is unclear as to whether the events are associated.

5.3.5.4 Persistent or Recurrent Adverse Events

A persistent adverse event is one that extends continuously, without resolution, between patient evaluation timepoints. Such events should only be recorded once on the Adverse Event eCRF. The initial severity (intensity or grade) of the event will be recorded at the time the event is first reported. If a persistent adverse event becomes more severe, the most extreme severity should also be recorded on the Adverse Event eCRF. If the event becomes serious, it should be reported to the Sponsor immediately (i.e., no more than 24 hours after learning that the event became serious; see Section 5.4.2 for reporting instructions). The Adverse Event eCRF should be updated by changing the event from "non-serious" to "serious," providing the date that the event became serious, and completing all data fields related to serious adverse events.

A recurrent adverse event is one that resolves between patient evaluation timepoints and subsequently recurs. Each recurrence of an adverse event should be recorded as a separate event on the Adverse Event eCRF.

5.3.5.5 Abnormal Laboratory Values

Not every laboratory abnormality qualifies as an adverse event. A laboratory test result must be reported as an adverse event if it meets any of the following criteria:

- Is accompanied by clinical symptoms
- Results in a change in study treatment (e.g., dosage modification, treatment interruption, or treatment discontinuation)
- Results in a medical intervention (e.g., potassium supplementation for hypokalemia) or a change in concomitant therapy
- Is clinically significant in the investigator's judgment

It is the investigator's responsibility to review all laboratory findings. Medical and scientific judgment should be exercised in deciding whether an isolated laboratory abnormality should be classified as an adverse event.

If a clinically significant laboratory abnormality is a sign of a disease or syndrome (e.g., alkaline phosphatase and bilirubin $5 \times$ upper limit of normal [ULN] associated with cholestasis), only the diagnosis (i.e., cholestasis) should be recorded on the Adverse Event eCRF.

If a clinically significant laboratory abnormality is not a sign of a disease or syndrome, the abnormality itself should be recorded on the Adverse Event eCRF, along with a descriptor indicating whether the test result is above or below the normal range (e.g., "elevated potassium," as opposed to "abnormal potassium"). If the laboratory abnormality can be characterized by a precise clinical term per standard definitions, the clinical term should be recorded as the adverse event. For example, an elevated serum potassium level of 7.0 mEq/L should be recorded as "hyperkalemia."

Observations of the same clinically significant laboratory abnormality from visit to visit should only be recorded once on the Adverse Event eCRF (see Section 5.3.5.4 for details on recording persistent adverse events).

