4.3.2.1.1 Dose Adjustments of Mircera

Dose adjustments may be performed during the entire study. The dose of Mircera should be adjusted to maintain the individual patient's Hb within a target range of ± 1 g/dL of his or her baseline Hb and between 10.0–12.0 g/dL. Baseline Hb is calculated as the mean of Hb values obtained at Visit 1 (Week –3) and Visit 2 (Week –1).

Dose adjustments should be performed at the scheduled dosing days and should be based on the Hb value measured on that day. They should not be performed more often than once every 4 weeks.

Dose adjustment rules for Mircera in response to Hb changes, including those required for safety reasons, are summarized in [Table 3](#).

Table 3 Mircera Dose Adjustments

Hemoglobin Assessment	Compared with the Previous Mircera Dose
Hb decreases by more than 1.0 g/dL compared with baseline Hb.	Increase dose by approximately 25% (or closest higher PFS strength).
Hb is less than 10 g/dL and greater than or equal to 9 g/dL (Hb < 10.0 and ≥ 9.0 g/dL).	Increase dose by approximately 25% (or closest higher PFS strength).
Hb is less than 9 g/dL (Hb < 9.0 g/dL).	Increase dose by approximately 50% (or closest to 50% increase PFS strength).
Hb increases by more than 1.0 g/dL compared with the baseline Hb.	Decrease dose by approximately 25% (or closest lower PFS strength).
Hb is increasing and is approaching 12 g/dL or Hb is greater than or equal to 12 g/dL (Hb ≥ 12 g/dL).	Decrease dose by approximately 25% (or closest lower PFS strength).
If Hb exceeds 12 g/dL and continues to increase following a dose reduction.	Stop doses until Hb is less than 12.0 g/dL. Resume dose at approximately 25% below previous dose (or closest lower PFS strength) at next scheduled dosing day.

Hb = hemoglobin; PFS = *prefilled syringe*..

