5.2.1 Adverse Events

According to the ICH guideline for Good Clinical Practice, an adverse event is any untoward medical occurrence in a clinical investigation subject administered a pharmaceutical product, regardless of causal attribution. An adverse event can therefore be any of the following:

- Any unfavorable and unintended sign (including an abnormal laboratory finding), symptom, or disease temporally associated with the use of a medicinal product, whether or not considered related to the medicinal product
- Any new disease or exacerbation of an existing disease (a worsening in the character, frequency, or severity of a known condition) (see Section 5.3.5.8 and Section 5.3.5.9 for more information)
- Recurrence of an intermittent medical condition (e.g., headache) not present at baseline
- Any deterioration in a laboratory value or other clinical test (e.g., ECG, X-ray) that is associated with symptoms or leads to a change in study treatment or concomitant treatment or discontinuation from study drug
- Adverse events that are related to a protocol-mandated intervention, including those that occur prior to assignment of study treatment (e.g., invasive procedures such as blood sampling, discontinuation of medications)

Kidney transplantation and routine diagnostic procedures/tests are not considered adverse events and should therefore not be recorded on an Adverse Event eCRF page.

The start of dialysis or the change in dialysis modality should not be considered an adverse event and should be recorded on a specific eCRF page (see Section 5.3.5.11).

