#### **4.4.2 Adverse Events**

All AEs recorded in the CRF will be listed and classified by System Organ Class (SOC) and Preferred Term (PT). Events will be coded using the latest version of Medical Dictionary for Regulatory Activities (MedDRA). Adverse event severity will be graded according to the WHO Toxicity Grading Scale for determining the severity of adverse events (refer to Appendix 7 of the study protocol for details). AEs that occurred during the treatment period: from the first treatment dose until 28 days after last dose or until the final visit (whichever is latest) will be summarized. Standard safety analyses for all AEs, related AEs, serious AEs, fatal AEs and AEs leading to study drug modification or discontinuation or withdrawal from study will be performed in terms of frequency tables by event and patient.

All adverse events of special interest (AESI) will be presented. AESI include but are not limited to the following:

- Cases of potential drug-induced liver injury that include an elevated ALT or AST in combination with either an elevated bilirubin or clinical jaundice, as defined by Hy's Law (see Section 5.3.5.7 of study protocol)
- Suspected transmission of an infectious agent by the study drug, as defined below:

Any organism, virus, or infectious particle (e.g., prion protein transmitting transmissible spongiform encephalopathy), pathogenic or non-pathogenic, is considered an infectious agent. A transmission of an infectious agent may be suspected from clinical symptoms or laboratory findings that indicate an infection in a patient exposed to a medicinal product. This term applies only when a contamination of the study drug is suspected.

Adverse events related to covid-19 will be identified using the special covid-19 SMQ containing a narrow basket of preferred terms (PTs) to provide a more targeted list of events related to the SARS-CoV-2 virus. Only events occurring in the pandemic timeframe (1 Dec 2019 onwards) will be included in this list. A listing of such adverse events associated with covid-19 will be provided. For those patients with confirmed covid-19 infection or positive PCR test (9 preferred terms from the above SMQ) any other AEs occurring within  $\leq 7$  days before and  $\leq 30$  days after start date of the AE will also be considered as covid-19 associated events.

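### Read literally, the laboratory reporting rule makes planned Hb titration a reportable adverse event while also leaving it to judgment, so the SAP 4.4.2 tables may be inflated or inconsistent across sites

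*Protocol*

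**What the plan says.** **Reporting rule.** Protocol 5.3.5.5 states: "A laboratory test result must be reported as an adverse event if it meets any of the following criteria". One criterion is that the result "Results in a change in study treatment (e.g., dosage modification, treatment interruption, or treatment discontinuation". Clinical significance in the investigator's opinion is a separate criterion in the same list, so it is not a precondition for this one. Protocol 5.2.1 has a parallel trigger for a laboratory deterioration that "leads to a change in study treatment or concomitant treatment or discontinuation from study drug".

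**Titration rule.** Protocol 4.3.2.1.1: "Dose adjustments should be performed at the scheduled dosing days and should be based on the Hb value measured on that day". It adds: "Dose adjustment rules for Mircera in response to Hb changes, including those required for safety reasons, are summarized in" Table 3. The table does not mark which rows serve safety and which serve maintenance.

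**Limits on reporting.** Two sentences in 5.3.5.5 pull back. One is "Medical and scientific judgment should be exercised in deciding whether an isolated laboratory abnormality should be classified as an adverse event". The other is "Observations of the same clinically significant laboratory abnormality from visit to visit should only be recorded once".

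**Analysis.** SAP 4.4.2 tabulates all events, related events, serious and fatal events, and "AEs leading to study drug modification or discontinuation or withdrawal from study". It names the WHO scale (Protocol Appendix 7) as the only grading scale. Protocol 5.3.3 also provides Table 4, for events the WHO scale does not list or does not suit.

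**The concern.** In most trials a dose change prompted by a laboratory value signals a tolerability problem, and the reporting criterion is written for that case. Here a dose change prompted by Hb is ordinary treatment, and Hb is also the primary endpoint. A site that follows the wording would file an adverse event when it titrates as instructed. A site that relies on the judgment sentence would not.

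The table of events leading to drug modification is the most exposed, because a titration event enters it by definition. The related-event table is exposed too, since Protocol Table 5 treats an event as related unless stated grounds apply. With a single arm there is no control rate against which titration records would cancel out. With about 35 sites for about 40 patients (Protocol 9.4), 40/35 is roughly 1.1 patients per site, so differences in site practice cannot be told apart from differences between patients.

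**Working it through.** **1. Is there an exemption?** Protocol 5.2.1 and 5.3.5.11 exempt kidney transplantation, starting or changing dialysis, and expected progression of kidney disease. Protocol 5.3.5.10 covers Hb monitoring and loss of effect but does not say whether a titrated Hb value is an adverse event. No section exempts a Table 3 change.

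**2. The plan's own figure.** The documents give no expected number of titration events. The only related design figure is about 90% power with n = 26 and SD 1.5 g/dL (Protocol 6.1). Normal approximation: 2Φ(√26/1.5 − 1.645) − 1 = 2Φ(1.754) − 1 = 92.1%. A t-based simulation gives 90.4%. The figure reproduces and is not in dispute. It only supplies an SD ceiling, and that ceiling is for a change between period averages, not for a single reading.

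**3. Ceiling on dose changes.** Table 3 decisions after the starting dose fall at Weeks 5, 9, 13 and 17 (Protocol Appendix 1). 4 × 40 = 160 core-period decision points.

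**4. How often Table 3 would trigger (illustration).** Assumptions: baseline Hb uniform on 10–12 g/dL; deviation at each visit normal with mean 0 and SD s; no drift, dose feedback or withdrawal. A trigger is Hb < 10, Hb ≥ 12, or a change of more than 1.0 from baseline. The row on approaching 12 is not counted. Integrating over baseline:

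p(s) = 2Φ(−1/s) + s[φ(0) − φ(1/s)]

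At s = 1.0: 2 × 0.1587 + (0.3989 − 0.2420) = 0.474. At s = 0.7: 2 × 0.0766 + 0.7 × (0.3989 − 0.1438) = 0.332.

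**5. From triggers to records.** Because a repeated abnormality is recorded once, a new record is counted only when Hb is out of range on a side where it was not out at the preceding dosing visit. This was simulated with a visit-to-visit correlation of 0.5 (lower figure) or 0 (upper figure).

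| SD (g/dL) | p per visit | Triggers, 160p | Records, 40 patients |
|---|---|---|---|
| 0.5 | 0.218 | 35 | 23–28 |
| 0.7 | 0.332 | 53 | 34–43 |
| 1.0 | 0.474 | 76 | 47–60 |
| 1.5 | 0.624 | 100 | 59–75 |

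At SD 0.5, 49–55% of patients have at least one trigger; at SD 1.0, 88–91% do. For the 28 patients left after 30% withdrawal (40 × 0.7), the 34–60 records become 24–42.

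**6. If only falls count.** Protocol 5.2.1 speaks of deterioration, and an Hb rise is not plainly one, although 5.3.5.5 covers any result. The model is symmetric, so counting falls only halves the records: 17–30 in 40 patients at SD 0.7–1.0.

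**7. Grading.** Appendix 7 grades only low Hb, with Grade 1 at 9.5–10.5 g/dL. A rise has no grade there, nor does a fall of more than 1.0 that ends above 10.5. Protocol 5.3.3 sends such events to Table 4; SAP 4.4.2 does not mention Table 4.

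**The case against.** **The section does not intend this.** It opens by saying that not every abnormality qualifies, and it asks for judgment on isolated values. Protocol 5.3.5.9 counts a preexisting condition only if it worsens, and renal anemia is an entry criterion. The criterion speaks of dosage modification, whereas titration is usually called dose adjustment. *What stands:* sensible sites may well not report, which is why inconsistency is as likely as inflation. The wording distinction does not hold, because the criterion covers any change in study treatment and Protocol 4.3.2 uses dose modification for any change entered on the drug administration form. A fall in Hb is also a worsening of the preexisting condition.

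**The count is model-based.** *This stands.* Dose feedback would lower it. The uncounted approaching-12 row, any drift, and the up to six further dosing visits in the extension (Protocol Appendix 2) would raise it.

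**Stronger readings a reader might infer.** One is that every triggering Hb becomes its own event, giving 53–76 at SD 0.7–1.0. Those are triggers; the record-once sentence reduces them. Another is that an in-target Hb of 10.0–10.5 becomes a toxicity because of the Grade 1 band. It does not: the scale grades events already reported, and 71–97% of simulated readings in that band trigger no dose change. A fall from 11.6 to 10.4 does trigger one, but it is 1.2 below baseline and so outside that patient's own target. A third is that titration would dominate the safety tables; the documents give no count of other events to compare with.

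**The tables already help.** Preferred terms are shown, and dose changes are tabulated separately (SAP 4.3.2.2 and 4.3.2.4). *This stands in part:* neither shows how many drug-modification events were titration alone.

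**A blanket exemption would do harm.** *This stands.* It would also remove Table 3 changes made for safety reasons, and it would change collection part-way through a trial whose interim review was in September 2019.

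**Conclusion.** The point holds in a limited form. On its wording, Protocol 5.3.5.5 (and 5.2.1 for deteriorations) requires an adverse event report when Hb leads to a planned Table 3 change. No section exempts this, and the judgment sentence in the same section points the other way. The overall, related and drug-modification summaries could therefore be inflated or differ by site. If sites report literally, the illustrative size is about 34–60 records in 40 patients at SD 0.7–1.0 and about 23–75 at SD 0.5–1.5, under the assumptions listed; falls alone would give half. These are not predictions. The primary endpoint and the SAP 4.3.1 criterion for the conversion factor are unaffected. The change is worth making because it is cheap and the drug-modification table is otherwise hard to interpret in a single arm.

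**What to change.** 1. **SAP 4.4.2.** Present all events, related events and events leading to study drug modification twice: with and without Hb events whose only consequence was a Table 3 adjustment. Define that subset before database lock from the event term, the recorded action taken, the dosing-day Hb and the doses given.
2. **SAP 4.4.2 grading.** Align it with Protocol 5.3.3, so that Table 4 applies where the WHO item is absent or not appropriate.
3. **Protocol.** Reconcile 5.3.5.5 and 5.2.1 with 4.3.2.1.1 so that all sites apply one rule on whether a titration-only Hb value is an adverse event. Keep reportable any Hb value that meets another listed criterion, loss of effect, or a Table 3 change made for safety reasons. Table 3 does not mark those changes, so the sponsor must identify them.

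**Cost.** One extra table split on data already being collected. If the protocol wording changes during the trial, the report needs a note on when the collection rule changed and which patients fall on each side. Items 1 and 2 need no protocol amendment and remain useful even if enrollment has closed.

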5.3.5.6 Abnormal Vital Sign Values

Not every vital sign abnormality qualifies as an adverse event. A vital sign result must be reported as an adverse event if it meets any of the following criteria:

- Is accompanied by clinical symptoms
- Results in a change in study treatment (e.g., dosage modification, treatment interruption, or treatment discontinuation)
- Results in a medical intervention or a change in concomitant therapy
- Is clinically significant in the investigator's judgment

It is the investigator's responsibility to review all vital sign findings. Medical and scientific judgment should be exercised in deciding whether an isolated vital sign abnormality should be classified as an adverse event.

If a clinically significant vital sign abnormality is a sign of a disease or syndrome (e.g., high blood pressure), only the diagnosis (i.e., hypertension) should be recorded on the Adverse Event eCRF.

Observations of the same clinically significant vital sign abnormality from visit to visit should only be recorded once on the Adverse Event eCRF (see Section 5.3.5.4 for details on recording persistent adverse events).

